## **7.2. Study Specifics**

### **7.2.1. Dose Suspension, Modification, or Termination for ARIA Events**

#### *Discontinuation of Dosing for a Given Subject*

The central MRI reading center will report incident cases of ARIA-E and ARIA-H to both the Sponsor and the PI within a specified time after observing the finding on MRI per the imaging manual procedures. All cases of ARIA will be reviewed by the Sponsor and the PI; decisions on dosing continuation, interruption, or discontinuation will be based on clinical symptoms, and the MRI information provided by the central reader. IDMC notification rules will be outlined in the IDMC charter. Guidelines on the management and disposition of ARIA-E and ARIA-H cases (including the criteria to be met for the continuation, suspension/resumption, permanent discontinuation of dosing due to ARIA, resumption of dosing after dose suspension due to ARIA [including rules for titrating up to the assigned dose], and management of recurrent ARIA) are provided in the following subsections. Dosing may also be terminated at the discretion of the Sponsor for medical reasons. See Section 10.1 for the full list of criteria for discontinuing study treatment.

CONFIDENTIAL

The information contained herein may not be used, disclosed, or published without the written consent of Biogen MA Inc.

7.2.1.1. Disposition of ARIA-E Cases

Table 8: Disposition of ARIA-E Cases

Clinical Symptom Severity	ARIA-E Severity on MRI (Central Read)		
	Mild	Moderate	Severe
Asymptomatic	Continue dosing at current dose and schedule	Suspend dosing. Once ARIA-E resolves the subject may resume dosing at the same dose.	
Mild	Suspend dosing. Once ARIA-E and clinical symptoms resolve, the subject may resume dosing at the same dose.		
Moderate			
Severe			
Serious "other medically important event" only 			
Serious, except for "other medically important event" 	Discontinue Dosing		

 "Other medically important events" requiring dose suspension include SAEs that are not life-threatening (in the opinion of the Investigator), do not require inpatient hospitalization or prolongation of existing hospitalization, and do not result in significant/permanent disability or congenital anomalies/fetal defects, but may (in the opinion of the Investigator) jeopardize the subject or may require intervention to prevent one of the outcomes listed above and as described in Section 15.3.3.

 SAEs requiring permanent discontinuation of study treatment include those that are life-threatening (in the opinion of the Investigator), require inpatient hospitalization or prolongation of existing hospitalization, and/or result in persistent or significant disability/incapacity or a congenital anomaly/birth defect as described in Section 15.3.3.

- Subjects who develop **mild ARIA-E, per central MRI reading, with no clinical symptoms** at any time during the study may continue in the study at their current dose. Subjects should complete all scheduled clinic visits for assessments and, in addition, have an unscheduled visit for an MRI and MOCA as well as biomarker and PK sample collection approximately every 4 weeks until the ARIA-E has resolved per the centrally read MRI. The Sponsor may require that the subjects discontinue dosing or continue dosing at a lower dose level based on review of safety and MRI data.
- Subjects who develop **moderate or severe ARIA-E, per central MRI reading, with no clinical symptoms** at any time during the study will temporarily suspend treatment, but should complete all scheduled clinic visits for assessments and, in addition, have an unscheduled visit for an MRI and MOCA as well as biomarker and PK sample collection approximately every 4 weeks until the ARIA-E has resolved per the centrally read MRI. If the ARIA-E has resolved and the subjects remain asymptomatic, the subjects may resume treatment at the same dose. Only subjects who have not missed more than 4 consecutive doses will be allowed to resume treatment.

CONFIDENTIAL

The information contained herein may not be used, disclosed, or published without the written consent of Biogen MA Inc.

- Subjects who develop **mild, moderate, or severe ARIA-E, per central MRI reading, accompanied by mild, moderate, severe, or serious (“other medically important event” only) clinical symptoms** at any time during the study will temporarily suspend treatment, but should complete all scheduled clinic visits for assessments and, in addition, have an unscheduled visit for an MRI and MOCA as well as biomarker and PK sample collection approximately every 4 weeks until the ARIA-E has resolved per the centrally read MRI. If the ARIA-E has resolved and the clinical symptoms have resolved, the subject may resume treatment at the same dose. Only subjects who have not missed more than 4 consecutive doses will be allowed to resume treatment.
- Subjects who develop **mild, moderate, or severe ARIA-E, per central MRI reading, accompanied by serious (except “other medically important event”) clinical symptoms** at any time during the study will permanently discontinue treatment. Subjects should complete all scheduled clinic visits for assessments and, in addition, have an unscheduled visit for an MRI and MOCA as well as biomarker and PK sample collection approximately every 4 weeks until the ARIA-E has resolved per centrally read MRI.

See Section 7.2.1.6 for details on resumption of dosing when suspension occurs during the titration period and Section 7.2.1.7 for guidelines on resuming dosing after a recurrence of ARIA.

#### 7.2.1.2. ARIA-H (Microhemorrhage)

In this study, new incident microhemorrhages are defined as new incident microhemorrhages that occur on treatment and do not include microhemorrhages at baseline.

CONFIDENTIAL

The information contained herein may not be used, disclosed, or published without the written consent of Biogen MA Inc.

**Table 9: Disposition of ARIA-H (Microhemorrhage) Cases**

Clinical Symptom Severity	New Incident Microhemorrhages  (Central Read)		
	≥1 and ≤4	≥5 and ≤9	≥10
Asymptomatic	Continue dosing at current dose and schedule	Suspend dosing. Once ARIA-H is stable, the subject may resume dosing at the same dose.	Discontinue dosing
Mild	Suspend dosing. Once ARIA-H stabilizes and clinical symptoms resolve, the subject may resume dosing at the same dose.		
Moderate			
Severe			
Serious "other medically important event" only 			
Serious, except for "other medically important event" 	Discontinue dosing		

 New incident microhemorrhages = new incident microhemorrhages on treatment; does not include microhemorrhages at baseline.

 "Other medically important events" requiring dose suspension include SAEs that are not life-threatening (in the opinion of the Investigator), do not require inpatient hospitalization or prolongation of existing hospitalization, and do not result in significant/permanent disability or congenital anomalies/fetal defects, but may (in the opinion of the Investigator) jeopardize the subject or may require intervention to prevent one of the outcomes listed above as described in Section 15.3.3.

 SAEs requiring permanent discontinuation of study treatment include those that are life-threatening (in the opinion of the Investigator), require inpatient hospitalization or prolongation of existing hospitalization, and/or result in persistent or significant disability/incapacity or a congenital anomaly/birth defect as described in Section 15.3.3.

**Asymptomatic ARIA-H (Microhemorrhage)**

- Subjects who develop a **≥1 and ≤4 new incident microhemorrhage(s)** at any time during the study may continue treatment at the current dose.
- Subjects who develop **≥5 and ≤9 new incident microhemorrhages** occurring at any time during the study will temporarily suspend treatment, but should complete all scheduled clinic visits for assessments and, in addition, have an unscheduled visit for an MRI and MOCA as well as biomarker and PK sample collection every 2 weeks (±3 days) until the microhemorrhage is confirmed as stable per the centrally read MRI. A microhemorrhage is considered stable if it is unchanged between 2 consecutive MRIs including the initial detection MRI and the MRI performed 2 weeks (±3 days) later. Once the microhemorrhage is deemed stable, subjects may resume treatment at the same dose. Only subjects who have not missed more than 4 consecutive doses will be allowed to resume treatment.

CONFIDENTIAL

The information contained herein may not be used, disclosed, or published without the written consent of Biogen MA Inc.

- Subjects who develop  $\geq 10$  **new incident microhemorrhages** during the study will permanently discontinue treatment. Subjects should complete all scheduled clinic visits for assessments and, in addition, have an unscheduled visit for an MRI and MOCA as well as biomarker and PK sample collection every 2 weeks ( $\pm 3$  days) until the microhemorrhages are deemed stable per centrally read MRI.

#### **Symptomatic ARIA-H (Microhemorrhage)**

- Subjects who develop  $\leq 9$  **new incident microhemorrhages and mild, moderate, severe, or serious (“other medically important event” only [Section 15.3.3]) clinical symptoms** will temporarily suspend treatment, but should complete all scheduled clinic visits for assessments and, in addition, have an unscheduled visit for an MRI and MOCA as well as biomarker and PK sample collection every 2 weeks ( $\pm 3$  days) until the ARIA-H (microhemorrhage(s)) is confirmed stable per the centrally read MRI. Microhemorrhages are considered stable if they are unchanged between 2 consecutive MRIs including the initial detection MRI and the MRI performed 2 weeks ( $\pm 3$  days) later. Once ARIA-H (microhemorrhage) is deemed stable and the clinical symptoms have resolved, the subject may resume treatment at the same dose. Only subjects who have not missed more than 4 consecutive doses will be allowed to resume treatment.
- Subjects who experience **serious (except “other medically important event” [Section 15.3.3]) clinical symptoms associated with microhemorrhage(s)** will permanently discontinue treatment, but should complete all scheduled clinic visits for assessments and, in addition, have an unscheduled visit for an MRI and MOCA as well as biomarker and PK sample collection every 2 weeks ( $\pm 3$  days) until the microhemorrhage(s) is confirmed stable per centrally read MRI.
- Subjects who develop  $\geq 10$  **new incident microhemorrhages**, regardless of symptom severity, during the study will permanently discontinue treatment. Subjects should complete all scheduled clinic visits for assessments and, in addition, have an unscheduled visit for an MRI and MOCA as well as biomarker and PK sample collection every 2 weeks ( $\pm 3$  days) until the microhemorrhages are deemed stable per centrally read MRI.

See Section 7.2.1.6 for details on resumption of dosing when suspension occurs during the titration period and Section 7.2.1.7 for guidelines on resuming dosing after a recurrence of ARIA.

CONFIDENTIAL

The information contained herein may not be used, disclosed, or published without the written consent of Biogen MA Inc.

### 7.2.1.3. ARIA-H (Superficial Siderosis)

**Table 10: Disposition of ARIA-H (Superficial Siderosis) Cases**

Clinical Symptom Severity	New Incident Areas of Superficial Siderosis  (Central Read)		
	1	2	>2
Asymptomatic	Continue dosing at current dose and schedule	Suspend dosing. Once ARIA-H is stable the subject may resume dosing at the same dose.	Discontinue dosing
Mild	Suspend dosing. Once ARIA-H stabilizes and clinical symptoms resolve, the subject may resume dosing at the same dose.		
Moderate			
Severe			
Serious "other medically important event"  only 			
Serious, except for "other medically important event" 	Discontinue dosing		

 New incident superficial siderosis = new incident superficial siderosis on treatment.

 "Other medically important events" requiring dose suspension include SAEs that are not life-threatening (in the opinion of the Investigator), do not require inpatient hospitalization or prolongation of existing hospitalization, and do not result in significant/permanent disability or congenital anomalies/fetal defects, but may (in the opinion of the Investigator) jeopardize the subject or may require intervention to prevent one of the outcomes listed above as described in Section 15.3.3.

 SAEs requiring permanent discontinuation of study treatment include those that are life-threatening (in the opinion of the Investigator), require inpatient hospitalization or prolongation of existing hospitalization, and/or result in persistent or significant disability/incapacity or a congenital anomaly/birth defect as described in Section 15.3.3.

#### Asymptomatic ARIA-H (Superficial Siderosis)

- Subjects who develop a **single incident focal area of hemosiderosis (also referred to as superficial siderosis)** may continue treatment at the current dose, but must have an unscheduled visit for an MRI and MOCA as well as biomarker and PK sample collection every 2 weeks ( $\pm 3$  days) until the superficial siderosis is confirmed as stable per the centrally read MRI. Superficial siderosis is considered stable if it is unchanged between 2 consecutive MRIs, including the initial detection MRI and the MRI performed 2 weeks ( $\pm 3$  days) later.
- Subjects who develop **2 focal areas of hemosiderosis (superficial siderosis)** occurring at any time during the study will temporarily suspend treatment, but should complete all scheduled clinic visits for assessments and, in addition, have an unscheduled visit for an MRI and MOCA as well as biomarker and PK sample collection every 2 weeks ( $\pm 3$  days) until the ARIA-H (superficial siderosis) is confirmed as stable per the centrally read MRI. Superficial siderosis is considered

CONFIDENTIAL

The information contained herein may not be used, disclosed, or published without the written consent of Biogen MA Inc.

stable if it is unchanged between 2 consecutive MRIs including the initial detection MRI and the MRI performed 2 weeks ( $\pm 3$  days) later. Once the superficial siderosis is deemed stable, the subjects may resume treatment at the same dose. Only subjects who have not missed more than 4 consecutive doses will be allowed to resume treatment.

- Subjects who develop **>2 focal areas of hemosiderosis (superficial siderosis)** occurring at any time during the study must permanently discontinue treatment and should complete all scheduled clinic visits for assessments and, in addition, have an unscheduled visit for an MRI and MOCA as well as biomarker and PK sample collection every 2 weeks ( $\pm 3$  days) until the ARIA-H (superficial siderosis) is confirmed as stable per the centrally read MRI. Superficial siderosis is considered stable if it is unchanged between 2 consecutive MRIs including the initial detection MRI and the MRI performed 2 weeks ( $\pm 3$  days) later.

#### **Symptomatic ARIA-H (superficial siderosis)**

- Subjects who develop  **$\leq 2$  new focal areas of superficial siderosis and mild, moderate, severe, or serious (“other medically important event” only)** clinical symptoms will temporarily suspend treatment, but should complete all scheduled clinic visits for assessments and, in addition, have an unscheduled visit for an MRI and MOCA as well as biomarker and PK sample collection every 2 weeks ( $\pm 3$  days) until the ARIA-H superficial siderosis is confirmed stable per the centrally read MRI. Superficial siderosis is considered stable if it is unchanged between 2 consecutive MRIs including the initial detection MRI and the MRI performed 2 weeks ( $\pm 3$  days) later. Once the ARIA-H (superficial siderosis) is deemed stable and the clinical symptoms have resolved, the subjects may resume treatment at the same dose. Only subjects who have not missed more than 4 consecutive doses will be allowed to resume treatment.
- Subjects who experience **serious (except “other medically important event” [Section 15.3.3]) clinical symptoms associated with ARIA-H (superficial siderosis)** will permanently discontinue treatment, but should complete all scheduled clinic visits for assessments and, in addition, have an unscheduled visit for an MRI and MOCA as well as biomarker and PK sample collection every 2 weeks ( $\pm 3$  days) until the superficial siderosis is confirmed stable per centrally read MRI.

CONFIDENTIAL

The information contained herein may not be used, disclosed, or published without the written consent of Biogen MA Inc.

- Subjects who develop **>2 new focal areas of superficial siderosis** regardless of clinical symptom severity will permanently discontinue treatment, but should complete all scheduled clinic visits for assessments and, in addition, have an unscheduled visit for an MRI and MOCA as well as biomarker and PK sample collection every 2 weeks ( $\pm 3$  days) until the superficial siderosis is confirmed stable per centrally read MRI.

See Section 7.2.1.6 for details on resumption of dosing when suspension occurs during the titration period and Section 7.2.1.7 for guidelines on resuming dosing after a recurrence of ARIA.

#### 7.2.1.4. ARIA-H (Macrohemorrhage)

- Subjects who develop any new incident macrohemorrhage, regardless of symptom severity during the study, will permanently discontinue treatment, but should complete all scheduled clinic visits for assessments and, in addition, have an unscheduled visit for MRI and MOCA as well as biomarker and PK sample collection every 2 weeks ( $\pm 3$  days) until the macrohemorrhage is confirmed stable per centrally read MRI.

#### 7.2.1.5. Disposition of Coincident ARIA-H and ARIA-E Cases

Subjects who develop ARIA-H coincident with ARIA-E at any time during the study will follow the most restrictive guidelines. Prior to resuming treatment, where applicable, ARIA-E must resolve, ARIA-H must be deemed stable, and the subject must be asymptomatic. For example, if a subject experiences asymptomatic ARIA-H (1-4 microhemorrhages) coincident with ARIA-E assessed as moderate on MRI and accompanied by mild clinical symptoms, the dose should be suspended per the ARIA-E guidelines summarized in Table 11.

#### 7.2.1.6. Resumption of Study Treatment After Suspension due to ARIA

##### 7.2.1.6.1. MRI Monitoring

When treatment resumes after a dose suspension due to ARIA, an MRI and MOCA will be performed as well as biomarker and PK sample collection 2 weeks ( $\pm 3$  days) after the second administration of the restarted dose if they do not have a scheduled MRI occurring during this period. In addition, if treatment was suspended during the dose titration prior to the subject reaching the maximum assigned dose, an MRI and MOCA will be performed as well as biomarker and PK sample collected 2 weeks ( $\pm 3$  days) after the second administration of each increase in dose. MRIs will otherwise be performed as indicated in the Schedules of Events (Section 4.2).

##### 7.2.1.6.2. Dosing Upon Resumption of Study Treatment

Subjects who suspend treatment due to ARIA for the first time may resume treatment at the same dose if they meet the criteria as described in Sections 7.2.1.1 to 7.2.1.5. Subjects who suspend and then resume dosing after having already reached their assigned top dose level are to continue dosing at that dose level. However, if dosing is suspended during the dose titration period, the

CONFIDENTIAL

The information contained herein may not be used, disclosed, or published without the written consent of  
Biogen MA Inc.

subject (1) must receive at least 2 doses at the restart dose before titrating up to the next dose level and (2) must complete at least the required number of doses at that dose level per their assigned dosing regimen, as outlined in Table 11.

**Table 11: Resumption of Study Treatment Following Dose Suspension Due to ARIA During Titration**

Assigned Dosing Regimen (Maximum Dose)	Dose Level at Which ARIA Occurred	Number of Doses Prior to ARIA	Number of Doses Needed Before Going to the Next Higher Dose
ApoE ε4 (+)			
Low Dose (3 mg/kg)	1 mg/kg	1	2
High Dose (6 mg/kg)	1 mg/kg	1	2
	1 mg/kg	2	2
	3 mg/kg	1	3
	3 mg/kg	2	2
	3 mg/kg	3	2
	3 mg/kg	4	2
ApoE ε4 (-)			
Low Dose (6 mg/kg)	1 mg/kg	1	2
	1 mg/kg	2	2
	3 mg/kg	1	3
	3 mg/kg	2	2
	3 mg/kg	3	2
	3 mg/kg	4	2
High Dose (10 mg/kg)	1 mg/kg	1	2
	1 mg/kg	2	2
	3 mg/kg	1	2
	3 mg/kg	2	2
	6 mg/kg	1	2
	6 mg/kg	2	2

**7.2.1.7. Management After Recurrent ARIA (Dosing and MRI)**

If the subject has a second occurrence of ARIA (i.e., a second occurrence of ARIA-E or of ARIA-H, or ARIA-E and ARIA-H) that requires dose suspension, after the ARIA-E resolves or stabilizes, the subject is to resume dosing at the next lower dose and is to receive 2 doses at that

CONFIDENTIAL

The information contained herein may not be used, disclosed, or published without the written consent of Biogen MA Inc.

dose level (i.e., the restart dose) before titrating up to the next higher dose. Once dosing has resumed, the guidelines outlined in Table 11 apply, unless the subject has reduced from 1 mg/kg to placebo. In this case, the subject will remain on placebo for the duration of the placebo-controlled portion of the study. If a subject resumes treatment after ARIA, an MRI and MOCA will be performed as well as biomarker and PK sample collection 2 weeks ( $\pm 3$  days) after the second administration of the restarted dose, and 2 weeks ( $\pm 3$  days) after the second administration of each increase in dose unless the subject has a scheduled MRI during this period. MRIs will otherwise be performed as indicated in the Schedules of Events (Section 4.2).

If the subject experiences a third episode of ARIA that requires dose suspension, the subject must discontinue study treatment. Subjects who discontinue treatment are to remain in the study and continue all protocol-required tests and assessments.

Subjects who develop ARIA during the placebo-controlled period but continue or resume treatment at an active dose are eligible to enter the LTE period and will receive the lowest dose that they have tolerated during the placebo-controlled period. A subject who is switched to placebo but remains in the study may be titrated to aducanumab 1 mg/kg during the LTE period.

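### After a second ARIA episode, protocol v2.0 and v3.0 let dosing restart when ARIA-E merely stabilizes, although every other ARIA-E restart rule requires it to resolve

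*Protocol*

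**What the plan says.** Section numbers are those of v3.0 unless stated.

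Section 7.2.1.7 covers a second occurrence of ARIA that leads to suspension, whether ARIA-E, ARIA-H or both. Its restart instruction is that "after the ARIA-E resolves or stabilizes, the subject is to resume dosing at the next lower dose", with two doses at that level before titrating up again. In v2.0 the same words stand in Section 7.2.2.6.

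The general ARIA-E rules are stricter. For symptomatic ARIA-E, Table 8 reads "Suspend dosing. Once ARIA-E and clinical symptoms resolve, the subject may resume dosing at the same dose". Its row for asymptomatic moderate or severe ARIA-E also waits for resolution. The text of Section 7.2.1.1 says that a subject who develops suspension-level ARIA-E "at any time during the study will temporarily suspend treatment", and for symptomatic cases: "If the ARIA-E has resolved and the clinical symptoms have resolved, the subject may resume treatment at the same dose". It adds: "Only subjects who have not missed more than 4 consecutive doses will be allowed to resume treatment". It then sends the reader to "Section 7.2.1.7 for guidelines on resuming dosing after a recurrence of ARIA".

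For mixed cases Section 7.2.1.5 says: "Subjects who develop ARIA-H coincident with ARIA-E at any time during the study will follow the most restrictive guidelines". Before a restart, where applicable, "ARIA-E must resolve, ARIA-H must be deemed stable, and the subject must be asymptomatic".

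**The concern.** Two restart rules reach the same subject and set different imaging thresholds for ARIA-E. Take a subject whose second-episode edema is unchanged from one scan to the next but still present. Section 7.2.1.7, read literally, has that subject resume one dose level lower. Section 7.2.1.1 and Table 8 keep the subject off treatment.

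At stake is redosing with unresolved edema in someone who has already had ARIA twice. The looser wording stands in the very section to which 7.2.1.1 refers sites for recurrences, so a site following the cross-reference meets it first. A site that tried to apply it would also find no criterion for stable ARIA-E.

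**Working it through.** The protocol attaches no figure to this rule, so there is nothing to recompute. The check sets the clauses side by side.

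| Place (v3.0) | Episodes covered | What must happen to ARIA-E | What must happen to ARIA-H |
|---|---|---|---|
| Table 8 | Any | Resolve | Not addressed |
| 7.2.1.1 text | Any time in the study | Resolve | Not addressed |
| 7.2.1.2 and 7.2.1.3 | ARIA-H, not limited to a first episode | Not addressed | Be stable |
| 7.2.1.5 | Coincident, any time in the study | Resolve | Be stable |
| 7.2.1.7 | Second occurrence of ARIA-E, ARIA-H or both | Resolve *or* stabilize | Not mentioned |

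1. **Scope overlaps.** Sections 7.2.1.1 and 7.2.1.5 are not limited to first episodes, so a second episode falls under them and under 7.2.1.7 together.

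2. **The thresholds differ.** For ARIA-E, stabilizing is an alternative to resolving only in 7.2.1.7. Everywhere else ARIA-E has to resolve, and stability is the standard for ARIA-H alone.

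3. **Stable ARIA-E is undefined.** Sections 7.2.1.2 and 7.2.1.3 define stability for microhemorrhage and superficial siderosis: no change between the detecting scan and one about two weeks later. Section 7.2.1.1 has no counterpart for ARIA-E; its four-weekly MRI schedule runs until resolution.

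4. **The sentence does not fit its own scope.** It opens by covering ARIA-E, ARIA-H or both, yet its condition names only ARIA-E. A recurrence of ARIA-H alone gets no condition there. If the condition read as ARIA-E resolving or ARIA-H stabilizing, both the scope and the other sections would fit. That points to lost words rather than a deliberate relaxation.

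5. **History.** In v1.0, Section 7.2.1.1 and the coincident-case rule (7.2.1.3) already required ARIA-E to resolve, and there was no separate section on recurrence. The looser wording arrives with v2.0 Section 7.2.2.6, where it conflicts with v2.0 Sections 7.2.1.1 and 7.2.2.4, and v3.0 carries it over.

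6. **What is not in conflict.** Section 7.2.1.7 sets the next lower dose where Table 8 allows the same dose. Section 7.2.1.6.2 ties the same-dose restart to a first suspension, so this difference is intended.

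**The case against.** The strongest reply is that 7.2.1.7 is a special rule for recurrences. Section 7.2.1.1 refers recurrences to it, and 7.2.1.6.2 links the general criteria to a first suspension. This does not remove the contradiction. The reference to a first suspension can be read as fixing only the restart dose. Section 7.2.1.7 does not say that it relaxes the need for resolution, and a looser imaging threshold after a second event would run against the section's own sequence of same dose, lower dose, then stop.

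A second reply is that most of the apparent gap is silence. This is right, and it limits the point. A reader might infer that 7.2.1.7, by not mentioning symptoms, missed doses or coincident ARIA-H, drops those conditions after a recurrence. The documents do not support that. The conditions are stated without limit to a first episode, and 7.2.1.7 need not repeat them to leave them in force. Counting the conditions restated in each section would therefore measure drafting, not risk.

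A third reply is that the consequence is contained. Under Section 7.2.1 the sponsor and the principal investigator review every ARIA case, and dosing decisions rest on symptoms and the central MRI reading. The restart is one level lower, and a third suspension-level episode ends treatment. All of this stands and keeps the severity low. The follow-up MRI in 7.2.1.7 helps less: it falls two weeks after the second restarted dose, so it does not gate the restart.

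Finally, v4.0 is the latest version in the file, and its supplied text ends in the long-term extension schedule. Its contents list still shows 7.2.1.7, and Table 3 still refers to it. A reader might infer that the wording persists; neither persistence nor correction can be shown.

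**Conclusion.** The point holds in a narrow form. In v3.0 Section 7.2.1.7, and identically in v2.0 Section 7.2.2.6, allowing ARIA-E to stabilize contradicts Table 8 and Sections 7.2.1.1 and 7.2.1.5 (v2.0: Table 8, 7.2.1.1 and 7.2.2.4). The same sentence leaves a recurrence of ARIA-H alone without a stated condition. It is probably a drafting slip, but as printed it permits a restart with unresolved edema.

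Severity is minor. The documents give no basis for the number of subjects or infusions affected, and power and type I error do not change. The conclusion rests on reading the any-time wording of 7.2.1.1 and 7.2.1.5 as including recurrences, and it is shown for v2.0 and v3.0 only.

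**What to change.** In Section 7.2.1.7, replace the restart condition with: *after ARIA-E has resolved and/or ARIA-H is deemed stable (as applicable) and the restart criteria of Sections 7.2.1.1 to 7.2.1.5 are met*. Keep the restart at the next lower dose. Check v4.0 Section 7.2.1.7 and make the same change there if the wording persists.

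The cost is one clause and a note to sites, with no effect on sample size, power or type I error. Waiting for resolution should seldom end treatment by itself. Section 5.1.2 reports that most ARIA-E in Study 221AD103 resolved 4 to 12 weeks after onset. With dosing every 4 weeks, the upper figure is 12 / 4 = 3 dosing intervals, against a limit of 4 consecutive missed doses. This assumes that recurrent episodes resolve about as fast as those reported, which the protocol does not state.
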